## 4.3 Study Recruitment and Payment

Potential participants will be identified through community activities, health fairs, advertisements and mail out announcements. To recruit minorities, we will perform blood pressure screening activities in targeted community barbershops and beauticians, where information about the study will be provided. We have previously used barbershops and beauticians for recruitment of African Americans into a hypertension study with significant success. Below we describe our recruitment venues:

- (i) The Emory Alzheimer's Disease Research Center (ADRC) Clinical Core registry of research participants will be utilized for recruitment. The registry includes about 400 individuals who have consented to participate in annual detailed research assessments with neuropsychological testing, neurological examination, and other components of a national uniform data set for the NIH designated Alzheimer's disease centers. This group of subject includes about healthy elderly individuals without cognitive symptoms or decline (controls, n= $\sim$ 100)), as well as subjects with mild symptoms and memory loss (mild cognitive impairment, n= $\sim$ 150), and Alzheimer's disease (n= $\sim$ 100). All subjects are interested and highly motivated to participate in research studies and have consented to be contacted.

(ii) Community-based recruitment: This will include announcement and recruitment information in periodicals and local newspapers. Blood pressure education sessions in local communities eg churches or barbershops will also be conducted.

(iii) Physician recruitment: Local physicians (primary care or specialty physicians) will be informed of the study and its requirements and provided information about referral to the study personnel. In addition, flyers for the study will be posted at outpatient areas in the following facilities: Emory University Hospital, Emory Clinic, Grady Memorial Hospital, and the VA medical Center if possible.

(iv) Study Visit Compensation:

- Screening visit with consent and cognitive testing only- \$10 gift card.
- Screening visit with consent, cognitive testing, physical exam, and blood sample- \$25 gift card.
- Baseline visit- \$75 gift card, 3 and 6 month follow up visits- \$25 gift card, 12 month follow up visit- \$75 gift card.
- No compensation will be given during the blood pressure medication adjustment visits.
  
- Transportation Reimbursement: A parking validation ticket (\$6 value) will be given to those subjects who drive and park at the Lowergate parking deck for the ACTSI portion of the study. Patients who require taxi service to the study visits can be reimbursed up to \$50 each way (Total of \$100 per visit). This payment will also be given in the form of gift cards.

## **5. STUDY INTERVENTIONS**

### **5.1 Interventions, Administration, and Duration**

Participants will be randomized into either candesartan or lisinopril treatment groups. Treatment will be provided in a capsule format to be taken once a day orally. Both candesartan and lisinopril will be formulated into identical capsules. Investigators, study personnel and participants will be blinded for drug assignment. Participants will be treated for 1 year.

### **5.2 Handling of Study Interventions**

The drugs will be stored in the medication room in the Investigational Drug Service (IDS) Pharmacy. The location of the IDS pharmacy is [name]. Access to the med room is limited to the IDS Pharmacists via a badge swipe. Accountability records are maintained for all investigational products (IP). Study medication bottles will be either delivered by courier to study site, get picked up by study personnel from the pharmacy, hand delivered to subjects, or mailed to subject's home. Subjects will receive 30, 45, or 90 day supply.

### **5.3 Concomitant Interventions**

The goal of the trial intervention is to achieve a blood pressure <140/90 mm Hg in at least 90% of the participants. To achieve blood pressure control, we will use a stepwise protocol as follows: candesartan 8 mg→16 mg→32 mg or lisinopril 10 mg→20 mg→40 mg. Both groups will also receive, if needed to achieve blood pressure control, HCTZ 12.5 mg→25 mg, Amlodipine 2.5 mg →5 mg→10 mg and metoprolol 12.5 mg→25 mg (extended release)→50 mg (extended release). Antihypertensive medications will be increased every 2 weeks until blood pressure control (less than 140/90 mm Hg) is achieved. Based on our prior study, we anticipate being able to achieve blood pressure control within 4-8 weeks in the majority of the participants. Only the candesartan and lisinopril treatments are blinded. The remaining treatments (HCTZ, Amlodipine, and Metoprolol) are open-label. In the instance where a participant cannot receive an add-on agent, e.g. if there is a history of allergy or intolerance to one of the add-on drugs (HCTZ, Amlodipine, and Metoprolol) or a contraindication due to drug-drug interaction (e.g. simvastatin dose >20 mg and amlodipine), then that add-on agent will be skipped and the next add-on drug will be used.

### **5.4 Allowed Interventions**

Participants will continue to receive their usual care from their regular primary physicians. Hypertension management will be addressed by the study physician (the PI).

## **5.5 Required Interventions**

In addition to the 2 study medications (candesartan and lisinopril), HCTZ, amlodipine, and metoprolol are allowed as described above to achieve blood pressure control to below 140/90 mm Hg. Medications will be adjusted up or down to maintain blood pressure control (<140/90 mm Hg) during the study period.

## **5.6 Prohibited Interventions**

Once participants are enrolled, addition of antihypertensive medications by non-study providers is not allowed. However, non-hypertensive medications are allowed as part of usual care. If a subject receives an antihypertensive medication from a non-study source after enrollment, the study physician will attempt to contact the prescribing provider, as long as the participant agrees, to explain the study protocol and request that all antihypertensive medications be prescribed through the study physician. If the participant or the provider does not agree to these recommendations, the participant will be withdrawn from the study for safety reasons.

## **5.7 Adherence Assessment**

Participants will be asked to bring their study medication bottles to the study center at each visit. Medication compliance will be assessed using pill count during the titration and follow up periods. We will define a compliance rate for a time period, t, as the ratio of: (the used number of pill prescribed for the number of days t- number of pills remaining or unused for the time t/ number of pills prescribed for time t) multiplied by 100.

# **6. EXPERIMENTAL PROCEDURES AND MEASURES**

## **6.1 Questionnaires and lifestyle and anthropometric measures**

Study interviews will be conducted in English as necessary and include the following:

(1) Demographic, social and medical history data, as well as a medication inventory will be collected. All participants are asked to bring all their prescribed medication bottles. The medication inventory will be done by inspecting the participant medication and recording the name, dose, frequency and indication if known.

(2) Instrumental activities of daily living (IADL) scale .

(3) We will specifically evaluate functional abilities related to the executive cognitive function using the Dysexecutive Functioning Questionnaire (DEX). DEX is a 20-item questionnaire, which is completed by the participant and study partner and is designed to assess everyday signs of executive difficulties.

(4) Weight and height (stadiometer to measure height with the subjects standing and balance beam scale to measure weight without shoes).

(5) Short Physical Performance Battery [SPPB: ability to stand with the feet side-by-side, semi-tandem, and tandem, time to walk 8 feet (measured twice), and time to rise from a chair and return to the seated position 5 times) which assesses balance, gait, strength of the lower extremities, and endurance in older persons];

(6) Physical activity will be assessed using the Physical Activity Scale for the Elderly (PASE), which measures occupational, household, and leisure activities during a one-week period and has high reliability in older adults.

## **6.2. Blood pressure measurement**

(1) Office blood pressure will be measured according to the American Heart Association guidelines: sitting position, rested for 5 minutes, appropriate cuff size (covering 60% of upper arm length and 80% of arm circumference), correct cuff placement (1-2 inches above brachial pulse on bare arm), and use of the bell of the stethoscope. Blood pressure will be measured in both arms. The arm with the higher blood pressure will be used throughout the study. We will obtain 2 seated followed by standing blood pressure measurements at 1 and 3 minutes during each visit.

### **6.3 Neuropsychological assessment:**

(i) Executive function will be assessed using the NINDS-initiated EXecutive Abilities: Measures and Instruments for Neurobehavioral Evaluation and Research or “EXAMINER” tool box. This test battery reliably and validly assesses executive function in clinical trials [<http://examiner.ucsf.edu/>]. The battery includes 11 tasks that generate 15 primary variables. Within this set, the EXAMINER investigators identified tasks measuring four domains that fit well in a single factor model of executive function: working memory, inhibition, set shifting, and fluency. The EXAMINER battery has excellent psychometric properties with test-retest reliability of over 0.9 and correlates by over 0.60 with an informant-based measure of day-to-day executive functioning, the Frontal Systems Behavior Scale. The parts of EXAMINER that we selected include:

- 1) Flanker task (inhibition) which involves responding to a central stimulus while ignoring flanking stimuli that are either compatible or incompatible with the central stimulus.
- 2) Set-shifting, a measure of mental flexibility assessing the subject's ability to attend to the specific attributes of compound stimuli, and to shift that attention when required.
- 3) Spatial 1-Back test assesses spatial working memory and
- 4) Dot Counting test assesses verbal working memory.
- 5) Verbal Fluency will be tested using a List Generation test which require the participant to generate words beginning with a specific letter, and category fluency in which the participant generates words from a specified category (e.g., animals, fruits).

Data will be scored using an open source web-based data management and scoring system available through the EXAMINER project Using item response theory, a single composite executive function score will be calculated from the available data points.

(ii) To assess additional cognitive domains/mood, we will use these tests included in the National Alzheimer's Coordinating Center Uniform Data Set.

- 1) Hopkins Verbal Learning Test will be used to assess memory domains.
- 2) Digit Span Test (DST) is a brief task that assesses attention.
- 3) Boston Naming Test assesses language by measuring ability of naming a visual confrontation drawing (15 items).
- 4) Trail Making Test: will be used as an additional measure of executive function.
- 5) Center for Epidemiologic Studies Depression Scale (CESD), and consists of 20 items, each scored from 0 to 3 points and higher scores indicate greater depressive symptoms.

### **6.4 Brain MRI imaging protocols**

MRI protocols are performed in 50-60 minutes and will be conducted at The Center for Systems Imaging (CSI). Table 1 provides the details of the imaging protocol.

Table 1: Neuroimaging sequences and scanner time

	Orient.	Voxel Size [mm]	Scan Time [min]	
Localizer			29 sec	
T1 MPRAGE	Sagittal	1.0x1.0x1.0	8 min 37sec	
3D T2 TSE SAG SPACE	Sagittal	1.0x1.0x1.0	6 min 58 sec	
BOLD CVR	Axial	3x3x3	6 min 9 sec	1off-1on-1off-1on-2 off C02
Remove Mask				
3D T2 FLAIR SPACE	Sagittal	1.0x1.0x1.0	7 min 59 sec	
2dPCASL	Axial	3.4x3.4x5 (1mm gap)	6min 11 sec	
DTI Axials	Axial	2x2x2	4 min 52 sec	30 directions
rs-fMRI	Axial	3.0x3.0x3.0	8 min 9 sec	
GRE Field Map	Axial	3.0x3.0x3.0	1 min 20 secs	
Neck Coil scans for labeling efficiency				
3D TOF MRA Carotids	Axial obliq	0.6x0.6x1.5	1 min 21 sec	
2D Phase Contrast	Axial obliq	0.7x0.7x5	27 sec	
Total Scan Time			53	

## 6.5 Vascular measures

(i) Carotid intima-media thickness and arterial stiffness: High-resolution B-mode ultrasonograms of the right common carotid artery will be obtained using a 7.5-MHz linear-array transducer attached to a digital ultrasound system. Participants are placed in a supine position with the head rotated to the left by using a 45-degree head block. Longitudinal images of the common carotid will be obtained. Indices of arterial stiffness and wave reflections will be estimated in the supine position using the Sphygmocor device (Atcor Medical, Australia), which records sequential high-quality pressure waveforms at peripheral pulse sites using a high-fidelity tonometer. Pulse-wave velocity (PWV) measured between carotid and femoral arteries is a regional assessment of aortic stiffness and is the gold standard index of arterial stiffness. Digital pulse amplitude tonometry (PAT) will be used to measure pulse volume amplitude (PVA) in the tip of the index finger, with participants resting in the supine position in a quiet, temperature-controlled environment and during reactive hyperemia, which will be elicited by the release of an upper arm blood pressure cuff inflated to suprasystolic pressure for 5 minutes. The Endo-PAT (Itamar-Medical, Israel) will be used to measure PAT. The reactive hyperemia index (RHI) will be calculated as the ratio of the post- to pre-occlusion pulse volume amplitude (PVA) of the tested arm, divided by the post- to preocclusion ratio of the control arm (the average PVA over a 1-minute interval starting 1-minute after cuff deflation divided by the average PVA measured for 1 minute before cuff inflation [baseline]).

(ii) Inflammation, endothelial function markers, and APOE: We selected inflammatory biomarkers based on the evidence that the marker may be associated with cognition and/or is affected by RAS/ARB. Various studies have suggested that these inflammatory markers are associated with cognitive function, increased in hypertension, and modulated by Ang II: C-reactive protein (CRP), cytokines (TNF- $\alpha$ , interleukin family), vascular adhesion molecules (ICAM, VCAM, E- and P-selectin), metalloprotease 9 (MMP9) fibrinogen, von Willebrand factor (vWF) and plasminogen activator inhibitor-1 activity (PAI-1). Endothelial progenitor cells (EPC) will be measured according to methods previously described. Mononuclear cells will be first isolated by density gradient from 10 cc of blood. EPC will be identified by the expression of surface antigens CD34+KDR+ which provides the best balance between cell count and accuracy (ICC=0.81, CV<10%), and reported as the number of cells per cytometric event to avoid error inflation due to variation in total blood cells. We will use EPC and adhesion molecules to further investigate the association between cerebrovascular reactivity and endothelial function. EPC measurement will be completed at ECCRI ([name]) at Emory and inflammatory markers and urinary proteins (including isoprostanes) will be done at the University of Southern California or the Foundation for Health Improvement and Technology (FHIT). Blood/urine samples will be stored at ACTSI then mailed to USC or FHIT in batches. We will perform baseline, 12 months assessments of the inflammatory biomarkers and baseline, 6 and 12 months assessments of the EPC

and urine chemistries. Blood samples will be drawn at baseline for APOE genotype as well. APOE will be performed USC or FHIT.

## 6.6 Blood chemistries and blood count,

Blood chemistries including electrolytes (potassium, sodium, chloride and bicarbonate as well as calcium and blood urea nitrogen (BUN), and creatinine) will be measured at baseline and during the follow-up as part of the safety monitoring for hyperkalemia and renal insufficiency, as shown in Table 2. A complete blood count will also be collected at baseline and 6, and 12 months. Blood will be drawn after application of a tourniquet, by use of a small gauge needle, from an ante-cubital vein, and by an appropriately trained professional from subjects. These are part of assessing safety of the study drug and will be performed at the local Emory Clinical Laboratory.

## 7. STUDY SCHEDULE

### 7.1 Schedule of Evaluations

The flow of the participants from screening to exit is described diagrammatically in figure 4 and the list of study procedures performed at each visit is detailed in Table 2.

**Table 2: Study procedures at various stages of the study**

Phase:	Screening/Enrollment		Baseline	Titration	Follow-up		
Number of visits	Phone	1	1	3-5	3		
Months	0	2-4w	1	2-3	3	6	12
Informed Consent	X						
Study forms	Screen1	Screen2	Baseline	FU-tit	FU3	FU6	FU12
UBACC	X						
Phone contact/frequency*	X	W			M	M	M
Screening Cognition and FAQ	X						
Letter to PMD	X						X
Antihypertensive taper	X						
H&P	X		X				
Medication inventory	X		X	X	X	X	X
Weight			X	X	X	X	X
Height			X				X
Blood pressure	X		X	X	X	X	X
BMP	X			X**	X	X	X
CBC			X			X	X
IADL, SPPB, DEX , CESD			X				X
Neuropsychological measures			X			X	X
Brain MRI			X				X
Vascular imaging			X				X
APOE			X				
EPC & Urine Chemistries			X			X	X
Inflammatory markers			X			X	X
Screening for AE/SAE				X	X	X	X
Time estimate, in minutes	15	40-60	210-240	20-30	20-30	60-90	210-240

\*: Frequency is at least once or twice per week (W) during tapering pre-visit antihypertensive medications and Monthly (M) during the FU phase.

\*\* : BMP during titration is either at 2 weeks (if only step one is needed) or 4 weeks if step 2 is needed

Study Visit Windows Table:

Baseline	Within 1 week of completed tapering; patient should not be off BP meds for longer than 1 week.
Med adjustment/Titration	+/- 3 days of 2 week visit after BL
Med adjustment/Titration	If blood pressure is not regulated at first titration visit, must return +/- 3 days of next 2 week visit- return every 2 weeks until BP is regulated.
3 month F/U	+/- 2 weeks of scheduled visit
6 month F/U	+/- 2 weeks of scheduled visit
12 month F/U	+/- 2 weeks of scheduled visit

## 7.2 Description of Evaluations

7.2.1 Screening: Initial eligibility will be determined via phone interview.. This screening process will determine the specific inclusion and exclusion criteria that can be evaluated by self-report, including age, hypertension or blood pressure diagnosis, and prior medical issues detailed in the inclusion/exclusion criteria. Data collected during this interview will be stored de-identified for future data analysis with no links to the patient or their PHI. A study ID number will be used to collect data and will not be linked to the participant. Those who are eligible via phone interview will be invited for a clinic screening visit along with their next-of-kin, if possible. The screening visit will include: explaining study details and obtaining informed consent, cognitive assessment, medical history, current medications, 2 seated blood pressure measurements, and baseline metabolic panel. Eligible participants currently receiving antihypertensive medications who agree to stop antihypertensive medications will be instructed on a taper protocol and asked to return for baseline evaluation and randomization.

7.2.2 Consenting Procedure: A signed consent form will be obtained from each participant or the participant's legally authorized representative. A single informed consent form will describe both the screening and study procedures. The consent form will describe the purpose of the study, the procedures to be followed, and the risks and benefits of participation. A copy will be given to each participant and this fact will be documented in the participant's study record and the participant's medical record as per Emory University policy. During the consenting process, an assessment for decisional capacity to participate in clinical research will be performed. A validated brief instrument for decisional capacity assessment will be administered: The University of California, San Diego Brief Assessment of Capacity to Consent (UBACC) instrument is a 10 item questionnaire that asks the participant about key areas of the informed consent. **A score greater than 14.5** correlates with a core of greater than 16 on the MacArthur Competency Assessment Tool for Clinical Research (MacCAT-CR). MacCAT-CR is the most validated instrument in assessing decisional capacity in clinical research and a score greater than 16 has been traditionally considered adequate in prior NIH studies. Participants who are deemed non-decisional but still qualify for the study will need to have a surrogate consistent with the intent of the Common Rule (45 CFR 46, Subpart A).The following are, in order, possible surrogates:

- (1) The person's agent designated by an advance health care directive.
- (2) The conservator or guardian of the person having the authority to make health care decisions for the person.
- (3) The spouse of the person.
- (4) The domestic partner of the person as defined in Section 297 of the Family Code
- (5) An adult son or daughter of the person.
- (6) A custodial parent of the person.
- (7) Any adult brother or sister of the person.
- (8) Any adult grandchild of the person.

(g) An available adult relative with the closest degree of kinship to the person.

When there are two or more available persons who are in different orders of priority pursuant to subdivision (c), refusal to consent by a person who is a higher priority surrogate shall not be superseded by the consent of a person who is a lower priority surrogate.

**7.2.3 Enrollment, Baseline, and Randomization:** During this phase, blood pressure measurements, detailed neuropsychological assessments, physical exam, brain MRI, and carotid ultrasound will be completed. Blood samples will also be collected for APOE, inflammatory and endothelial markers. Randomization and study intervention will occur after baseline data collection. Participants will then be started on the study medications. For all study related testing, the test results will not be disclosed to you unless deemed necessary by the study Physician.

**7.2.4 Follow-up Visits:** Following randomization, participants will be seen every two weeks, where antihypertensive study medications will be increased until they achieve blood pressure control (<140/90 mmHg), according to the designated trial protocol for blood pressure control. Blood pressure, heart rate, weight, adverse events (AE) and serious adverse events (SAE), pill count (to assess compliance), and use of non-study medications data will be collected. Once hypertension control is achieved, participants will be seen at 3, 6 and 12 months visits. Repeat neuropsychological assessment, blood draws (EPC and inflammatory markers), and urine collection will be conducted at the 6 and 12 months visit. Repeat neuroimaging and vascular ultrasound will be repeated at 12 months. BMP will also be checked at 2 weeks after randomization if only step one is needed, 4 weeks post randomization if treatment beyond step 1 is needed, and at 3, 6 and 12 months as shown in **Table 2**. Participants will also be contacted by phone as described in Table 2, Monthly during the follow-up phase. During these phone calls, participants will be asked about missing any doses in their medications and screened for any potential adverse events.

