## 4.2 Exclusion Criteria

- (1) Intolerance to candesartan or lisinopril ;
- (2) SBP >200 or DBP >110 mm Hg;
- (3) Renal disease or hyperkalemia (SCr >1.99 mg/dl or K > 5.5 meq/dl);
- (4) Active medical or psychiatric problems (An active problem is one that requires medical attention and is deemed as a safety risk by the study physician, for example current cancer treatment, infections such as pneumonia, current gastrointestinal or other internal bleeding, HIV treatment, hematological disease, Parkinson's disease, multiple sclerosis)
- (5) Uncontrolled congestive heart failure [shortness of breath at rest or evidence of pulmonary edema on exam];
- (6) History of stroke in the past 3 years (self-reported clinical stroke within the past 3 years/ incidental infarcts on MRI scanning is allowed);
- (7) Inability to perform the study procedures (those with contraindications for MRI will be enrolled but will not undergo the MRI; those with history of asthma, COPD, or significant pulmonary disease will not undergo the CO2-reactivity protocol);
- (8) Women of childbearing potential
- (9) Current use of acetylcholine-esterase inhibitors or NMDA receptor antagonist (memantine) or a diagnosis of dementia self-report or care-giver report
- (10) In those who lack decision capacity, a *study surrogate* who can sign on their behalf will be required. Since we are enrolling only those with MCI, we anticipate that most participants will have decision capacity
- (11) Current use of Lithium, as most antihypertensive classes may lead to increased lithium toxic levels.

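### Only one safety BMP is scheduled during titration, so the top study-drug dose and both HCTZ doses can run to month 3 without a planned potassium or creatinine check

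*Combined protocol and SAP*

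**What the plan says.** **BMP schedule.** Section 7.2.4 sets one draw at 2 weeks for participants who need only step one; for the others it is "4 weeks post randomization if treatment beyond step 1 is needed, and at 3, 6 and 12 months". The Table 2 footnote agrees: "BMP during titration is either at 2 weeks (if only step one is needed) or 4 weeks if step 2 is needed". Section 8.2 lists draws at baseline and at months 1, 3, 6 and 12, and lets the PI or the primary care physician order further tests where they see a need.

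**Titration.** Section 5.3 gives three study-drug levels (candesartan 8, 16, 32 mg or lisinopril 10, 20, 40 mg). It then lists the add-ons, beginning with HCTZ 12.5 and 25 mg. The pace is fixed: "Antihypertensive medications will be increased every 2 weeks until blood pressure control" is reached. The add-ons are taken in turn, since for a drug a participant cannot take, "that add-on agent will be skipped and the next add-on drug will be used". On duration, "we anticipate being able to achieve blood pressure control within 4-8 weeks in the majority of the participants". The row "Number of visits" in Table 2 shows 3-5 for titration, and the visit windows table has uncontrolled participants "return every 2 weeks until BP is regulated".

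**Risks and limits.** Section 8.1 names kidney failure and high potassium for both study drugs, and kidney failure, volume depletion and low potassium for HCTZ. Section 4.2 excludes people with creatinine above 1.99 mg/dl or potassium above 5.5. Section 9 ends treatment at creatinine above 2.5 mg/dl or potassium above 5.8.

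**The concern.** The early schedule follows a sensible pattern. A participant who stays on the starting dose is tested two weeks after it begins. The middle dose begins at week 2 and is tested at week 4, again two weeks later. The pattern then stops just as exposure rises: the top dose of the renin-angiotensin drug and the diuretic added to it get no corresponding test before month 3.

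The section 9 limits are laboratory values. Blood pressure readings, adverse event questions, pill counts and monthly calls do not measure them. A participant could therefore pass a stopping limit during the steepest part of the escalation without anyone knowing, unless a physician happened to order a test. What is at stake is participant safety; no statistical figure in the plan depends on this point.

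**Working it through.** There is no figure in the plan to reproduce; the check is calendar arithmetic.

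**Inputs.** Increases every 2 weeks and the dose levels (5.3); the week 2 or week 4 BMP, then month 3 (7.2.4, Table 2); windows of ±3 days for titration visits and ±2 weeks for month 3 (visit windows table); 3-5 titration visits and a month row with baseline at month 1 (Table 2).

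**Assumption.** Each increase moves one level, in the order listed in 5.3.

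**Start weeks.** Level k starts at week 2(k − 1): study drug at weeks 0, 2 and 4; HCTZ 12.5 mg at week 6; HCTZ 25 mg at week 8. The week 4 BMP is drawn at the visit where the top dose would begin, so it reflects the middle dose.

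**When month 3 falls.** One month = 30.44/7 = 4.35 weeks. There are two readings:
- Table 2's month row: month 3 is two months after baseline, 2 × 30.44/7 = 8.70 weeks.
- From randomization: 3 × 30.44/7 = 13.046 weeks.

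The two windows together give ±(2 + 3/7) = ±2.43 weeks.

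**Weeks from each increase to the next scheduled BMP (range with windows).**

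| Increase | Start | Table 2 month row | From randomization |
|---|---|---|---|
| Top study-drug dose | week 4 | 8.70 − 4 = 4.7 (2.3 to 7.1) | 13.046 − 4 = 9.0 (6.6 to 11.5) |
| HCTZ 12.5 mg | week 6 | 8.70 − 6 = 2.7 (0.3 to 5.1) | 13.046 − 6 = 7.0 (4.6 to 9.5) |
| HCTZ 25 mg | week 8 | 8.70 − 8 = 0.7 (−1.7 to 3.1) | 13.046 − 8 = 5.0 (2.6 to 7.5) |

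The negative value means the month 3 draw would precede the increase.

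**Does the plan expect titration to last this long?** Three visits at two-week spacing end at week 3 × 2 = 6, and five end at week 5 × 2 = 10. If control is seen at the last visit, the last increase was made one visit earlier: at week 4 (top dose) with three visits, week 6 (HCTZ 12.5 mg) with four, and week 8 (HCTZ 25 mg) with five. Table 2 therefore provides for all three increases.

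**Margin at the entry limits.** Creatinine 2.5 − 1.99 = 0.51 mg/dl; potassium 5.8 − 5.5 = 0.3 meq. This is the extreme case; most participants will start further away.

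**The case against.** The strongest reply is that the size of the gap rests on inference.

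- **Dose order.** The plan does not define step one or step 2, and does not say that every study-drug level precedes HCTZ or that each visit moves one level. One level per visit through the whole ladder is 3 + 2 + 3 + 3 = 11 levels ending at week 20, far beyond 3-5 visits. If a step moves more than one level, more of the escalation falls before the week 4 BMP. This stands as a limit on the exact weeks. However, if HCTZ came earlier, the top dose would move later and would still have no scheduled test before month 3.
- **Month 3.** On Table 2's row the waits are shorter, and for HCTZ 25 mg the month 3 draw comes sooner than the two weeks proposed here. That stands, and the proposed wording lets that draw count. The case of month 3 preceding the increase also fits poorly with 7.2.4, which places the month 3 visit after control is reached.
- **Expected duration.** Control at week 8 means the last increase was at week 6, so HCTZ 25 mg lies outside the 4-8 week expectation for the majority. That also stands; only Table 2's fifth visit reaches it.
- **Other safeguards.** Section 8.2 promises careful monitoring of chemistry, but as described elsewhere in the methods, which leads back to the same schedule. Further laboratory work under 8.4 follows an adverse event, and 8.8 follows up a raised value already found. Neither detects a silent change. Discretionary tests soften the gap without closing it.
- **Harm is not quantified.** The documents give no event rate and no number still being titrated after week 4.

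**Conclusion.** The concern holds. One BMP is scheduled during titration and the next is at month 3, while the top study-drug dose and both HCTZ doses can start at week 4 or later. For the top dose the nominal wait is 4.7 or 9.0 weeks, depending on how month 3 is counted. For HCTZ 12.5 mg it is 2.7 or 7.0 weeks, and for HCTZ 25 mg 0.7 or 5.0 weeks. These figures assume one level every two weeks in the listed order.

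No section requires a BMP after every increase, so this is a gap and not an inconsistency. Its consequence cannot be quantified from the documents. The change is still worth making, because the plan itself names the risks, sets laboratory stopping limits and already brings these participants in every two weeks.

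**What to change.** **Main change.** Add to 7.2.4 and to the Table 2 footnote:

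> During the titration phase, BMP is also drawn at the next two-weekly visit after the top study-drug dose is started and at the next two-weekly visit after HCTZ is started or increased, whether or not treatment is increased again at that visit. The month 3 BMP serves if it is drawn after that increase and at or before that visit.

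Each of these increases is then tested after 2 weeks (0.7 weeks for HCTZ 25 mg on Table 2's row).

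**Clerical alignment.** In 8.2, replace the list of draw times with: screening, during titration as in Table 2, and 3, 6 and 12 months. The present list shows a month 1 draw for everyone, whereas Table 2 tests step-one participants at week 2 and places the first draw at screening. Section 7.2.1 calls that screening draw a baseline panel, so this is only tidying.

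**Cost.** Wording in three places, and up to three draws per affected participant (weeks 6, 8 and 10), or two if month 3 falls at week 8.7. No visits are added, because an increase means blood pressure was not controlled and a return in two weeks is already required. If 10% to 50% of the 160 enrolled are affected (an assumption; the documents give no figure), that is 16 to 80 participants and at most 16 × 3 = 48 to 80 × 3 = 240 draws, or 32 to 160 at two each.

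**What it leaves open.** Section 5.5 allows upward adjustment throughout the year. An increase made after titration, for example soon after month 6, would still wait for the next scheduled BMP. The sponsor may wish to decide separately whether to cover those.
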